7.1.3 Payment

If the NIHR bid is successful, participants will be provided a voucher for their participation in the study.

7.2 Consent

The Chief Investigator (CI) retains overall responsibility for the conduct of the research, this includes the taking of informed consent of participants at their site. They must ensure that any person delegated responsibility to participate in the informed consent process is duly authorised, trained and competent to participate according to the ethically approved protocol, principles of Good Clinical Practice (GCP) and Declaration of Helsinki. If delegation of consent is acceptable then details should be provided.

Informed consent must be obtained prior to the participant undergoing procedures that are specifically for the purposes of the trial and are out-with standard routine care (including the collection of identifiable participant data unless the trial has prior approval from the Confidentiality Advisory Group (CAG) and the Research Ethics Committee (REC)).

The right of a participant to refuse participation without giving reasons must be respected.

The participant must remain free to withdraw at any time from the trial without giving reasons and without prejudicing his/her further treatment and must be provided with a contact point where he/she may obtain further information about the trial. Data and samples collected up to the point of withdrawal can only be used after withdrawal if the participant has consented for this. Any intention to utilise such data should be outlined in the consent literature. Where a participant is required to re-consent or new information is required to be provided to a participant it is the responsibility of the PI to ensure this is done in a timely manner.

The CI takes responsibility for ensuring that all vulnerable participants are protected and participate voluntarily in an environment free from coercion or undue influence.

If a participant cannot read or write, or will require a translator, or has a cognitive impairment, appropriate alternative methods for supporting the informed consent process will be employed. This 24

may include allowing a witness to sign on a participant's behalf (in the case of problems with reading or writing), or allowing someone to date the form on behalf of the participant, or providing Participant Information Sheets in other languages or in a format easily understood by the participant population (in the case of minors or cognitive impairment).

Translation should be conducted by an NHS interpreter from the local interpretation service. The interpreter should be present in person for the duration of the consent process. Written information must be translated by an independent service that is able to back translate the document independently.

Regardless as to participant background, language, or cognitive impairment, they should be able to discuss the research with a member of the team knowledgeable about the research about the nature and objectives of the trial and possible risks associated with their participation, as well as a competent individual that can translate or support the communication needs of the participant.

Written material, including the participation information sheet and consent forms will be sent to the REC for approval.

Following the onboarding process, participants will have 7 days to consider the information, and a further appointment to ask any questions, before giving informed consent.

All participants must have capacity to decide whether or not to consent to being a participant of the study. Individuals that do not have capacity to make this decision will not be able to participate in the study, due to the nature of the intervention.

A capable person will:

- o understand the purpose and nature of the research
- understand what the research involves, its benefits (or lack of benefits), risks and burdens
- o understand the alternatives to taking part
- o be able to retain the information long enough to make an effective decision
- be able to make a free choice
- be capable of making this particular decision at the time it needs to be made (though their capacity may fluctuate, and they may be capable of making some decisions but not others depending on their complexity)
- where participants are capable of consenting for themselves but are particularly susceptible to coercion, it is important to explain how their interests will be protected

A person is assumed to have the mental capacity to make a decision unless it is shown to be absent. Mental capacity is considered to be lacking if, in a specific circumstance, a person is unable to make a decision for him or herself because of impairment or a disturbance in the functioning of their mind or brain. In practice for participants with mental incapacity this means that they should not be included in clinical trials if the same results can be obtained using persons capable of giving consent and should only be included where there are grounds for expecting that their taking part will be of direct benefit to that participant, thereby outweighing the risks. The Mental Capacity Act 2005 does not apply to CTIMPs.

All these procedures will be taken into consideration in this study.

7.2.1 Consent Process

Participants that are referred to the study will be asked for consent to be contacted by a member of the community mental health team. If they consent to be contacted, a member of the MBT clincal team will contact them to arrange a face to face appointment. In this appointment the researcher will explain the participant information sheet to the participant, and answer any questions that the participant has about the study. They will be given 7 days to think about whether they would like to take part in the study. After this time, the team will contact them to determine whether they would like to consent to the study. The participant will be asked to read and sign the consent form, if they wish to be part of the study. They will be advised that they can withdraw consent at any time of the study without any risk to their clinical treatment. The consent forms will be scanned and stored securely on NHS servers, and the paper copy will be stored under lock and key until the end of the study. Both documents will be destroyed following the study.

7.3 Baseline data

Participants will be asked to provide demographic information about gender, age, and ethnicity at baseline. This will help the trial determine whether the study has been inclusive of a demographic representative of the local population.

Baseline data will also be taken for each of the 5 questionnaires used as outcome measures, and for data relating to service use, self-harm, and suicidality. This will enable the research study to sufficiently detect meaningful change.

Diagnostic data will also be taken – particularly pertaining to the results of each participant scores on the DSM-5 interview, SCID-5-PD, which will be used to determine whether the participant meets the inclusion criteria for the study.

7.4 Trial assessments

The timing of filling out the questionnaires will be:

- Weekly LPFS 2.0. and Social Isolation Short Form 4.0.
- Every six months ReQoL,10, Dialogue and CSRSS. Review of medical records to indicate changes to service use, self-harm, and suicidal behaviour.

All five questionnaires are taken as routine measures every 6 months in clinical treatment within the MBT service. The major change to the data collection is that the LPFS 2.0 and the Social Isolation Short Form 4.0 will be taken weekly.

7.5 Long term follow-up assessments

In the 6 months after the treatment phase the participant will be asked to fill out the primary outcome questionnaires (LPFS 2.0. and Social Isolation Short Form 4.0.) on a weekly basis and the secondary outcome questionnaires (ReQoL,10, Dialogue and CSRSS) at the end of the follow up period for the purpose of the scientific research.

7.6 Qualitative assessments

At the end of the follow up period, each participant will be asked to participate in a brief semi-structured interview. The purpose of this qualitative assessment will be two-fold. The first set of questions will be designed to determine the participants experience of being part of a long term research study, their experience of filling out weekly questionnaires, and their experience of adhering to the trial protocol. The second set of questions will be focused on the intervention, and will aim to understand the participants experience of the MBT programme generally, how relevant they felt MBT was to them as an older adult, their view on the impact MBT has had upon their mental health, as well as any adaptations or changes they think might be important to consider in future developments of MBT.

The qualitative assessments will be conducted by the CI, another member of the team or a person with lived experience at the end of the follow up period, in order to reduce any bias, or impact on participant's treatment. Clinicians will not interview participants that they have seen for individual therapy.

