3 OBJECTIVES AND OUTCOME MEASURES/ENDPOINTS

3.1 Primary Outcomes:

To evaluate the feasibility of MBT in older adults

Feasibility of the study will be assessed by examining recruitment rate, consent rate, proportion of participants lost to follow-up, number of sessions attended, and drop out rate. The detailed table in the

upload section of this application illustrates the feasibility aims. This table shows the aims for the study with regard to above metrics.

To evaluate the acceptability of MBT in older adults

Acceptability will be evaluated by using Semi-structured qualitative interviews. These interviews will be delivered by 2-3 lived-experience researchers. I aim to determine what adaptations are indicated, integrating findings from qualitative and quantitative analysis to assess the feasibility of MBT. This will result in a fully adapted intervention.

I will use the Theoretical Framework for Acceptability to ensure the interviews assess acceptability. The interviews will focus on the seven constructs of acceptability (Paynter et al 2023):

To evaluate the change in personality functioning and social isolation in older adults undergoing MBT.

Changes in Personality Functioning Using the Level of Personality Functioning Scale Brief Form (LPFS-BF 2.0)

The LPFS 2.0 is a 12-item questionnaire that assesses personality functioning on a 4-point scale (Bender et al., 2011). This tool offers insights into the severity of personality pathology and sheds light on self and interpersonal functioning (Hutsebaut et al., 2016). The LPFS 2.0 has been empirically validated for older adults and has proven valuable in assessing personality functioning in this demographic (Stone et al., 2021).

To ensure adequate statistical power, the LPFS-BF will be administered weekly, following each individual therapy session. This frequent data collection will enhance the reliability of observed changes.

Loneliness Measured by the Social Isolation Short Form 4a

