3.6 Exploratory endpoints/outcomes

Qualitative interviews will be conducted to determine acceptability. See section on qualitative methods.

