12 MONITORING, AUDIT & INSPECTION

Three areas of the study require monitoring. These include:

a) Consent, participant information onboarding process,

All initial appointments will be video recorded using MS Teams and stored. The video recordings will be reviewed for adherence to the protocol by the CI at the beginning of the study. All participants must be given all information in the participant information sheet verbally, as well as additional written copies to review following the first contact. Signed consent forms will be reviewed by the CI once at the beginning of the study for all participants. The CI will be based on site, where all of the initial contacts will occur.

b) Adherence to MBT treatment manual

All MBT individual and group sessions will be recorded. A sample of these recordings will be reviewed every 4 weeks by an accredited MBT supervisor. The research team will review tapes as peers throughout the programme, using the adherence checklist, as part of the weekly MBT clinical team meeting.

c) Data input, management, and storage.

The data collection team will be responsible for ensuring that the data collection, management, and storage accords with the study protocol. The CI for the study is part of the clinical team, and so will be unable to access the database containing outcome scores. As such the data collection team will peer review their adherence. The CI will supervise the members of the data collection team, ensuring that they are aware of the processes and procedures required. A named person external to the data collection team will monitor the database every 6 weeks for adherence to the protocol, and reporting any deviations to the CI.

d) GMMH R & I audit and monitoring

This study will be subject to audit and monitoring by GMMH's R and I team. This monitoring will occur in line with the relevant SOP (RDSOP11)

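### Sections 3.1 and 7.6 disagree on who conducts the acceptability interviews, and 7.6 does not bar a clinician who led the participant's MBT group from interviewing

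*Protocol*

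**What the plan says.** Section 3.1 places acceptability under the primary outcomes and names the instrument: "Acceptability will be evaluated by using Semi-structured qualitative interviews". It then names the interviewers, with no alternative: "These interviews will be delivered by 2-3 lived-experience researchers". The table in 3.7 also has acceptability in its primary block.

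Section 7.6 describes the interview at the end of follow-up, which covers both taking part in the research and the experience of MBT. On who conducts it: "The qualitative assessments will be conducted by the CI, another member of the team or a person with lived experience". The same sentence sets the timing at the end of follow-up and gives the reason: "in order to reduce any bias, or impact on participant's treatment". One exclusion follows: "Clinicians will not interview participants that they have seen for individual therapy".

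Section 12 states the CI's position: "The CI for the study is part of the clinical team, and so will be unable to access the database containing outcome scores". Section 8.1 gives each participant a 50-minute individual session and a 75-minute group session every week for 18 months, delivered by four clinicians. Section 10.2 describes one treatment group of eight patients, with a second planned for 2025. Section 7.7 offers an exit interview to everyone who withdraws and names no interviewer.

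**The concern.** Two current sections give different rules for the same interviews. A team following 7.6 could complete every end-of-study interview without a lived-experience interviewer; a team following 3.1 could not. Staff cannot tell which applies.

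The looser rule also lets people who delivered the therapy ask whether it was relevant and whether it helped. Participants may soften criticism in front of a clinician they have worked with, and section 13.10 says they can be referred back to the same service. The interviews are the only measure of acceptability in the 3.7 table, and 3.1 relies on them, together with the quantitative findings, to decide how MBT should be adapted. If treating clinicians collect these data, the analysis cannot later remove their influence.

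**Working it through.** No sample size, error rate or effect size is involved. The check sets the sections side by side.

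1. **Who may interview.** Section 3.1: two to three lived-experience researchers. Section 7.6: the CI, another team member, or a person with lived experience, joined by *or*. The second list contains the first and adds two kinds of interviewer. The rules differ.

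2. **Whether the added interviewers can be treating staff.** Section 12 puts the CI in the clinical team. The exclusion in 7.6 ("Clinicians will not interview participants that they have seen for individual therapy") would be needless unless clinicians could be interviewers. So treating staff are within the permitted set.

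3. **What the exclusion covers.** It covers individual therapy only. From 8.1, scheduled weekly contact is 50 + 75 = 125 minutes, of which the group is 75/125 = 60%. The exclusion is therefore silent on the component with more scheduled time.

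4. **How many clinicians remain eligible.** Section 8.1 gives four. Assume one individual therapist per participant, and that all four count as members of the team in 7.6 (neither is stated). Then 4 − 1 = 3 remain eligible for a given participant. How many of those three led that participant's group is not given; the possible range is 0 to 3. With four clinicians and one or two groups, overlap is a practical possibility, but the documents do not establish it.

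5. **What else protects the interview.** Section 7.6 places it at the end of follow-up to limit bias. The section 7 table agrees, giving 30–34 months. The flow chart is less clear: it lists the interview at the opening of the follow-up phase.

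6. **Other interviews.** Section 4 and the flow chart also plan interviews at the beginning. An exclusion based on having already seen the participant for individual therapy does little before treatment starts. The exit interviews in 7.7 have no interviewer rule.

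7. **Consistency with the protocol's own bias control.** Section 12 keeps the CI from the outcome scores because of the clinical role, yet 7.6 lists the CI first among the interviewers.

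8. **Status of acceptability.** Primary in 3.1 and 3.7. Exploratory in 3.6: "Qualitative interviews will be conducted to determine acceptability". Absent from the trial summary, where the primary objective is change in personality functioning and social isolation. Section 3.4 names those same two as the primary measures.

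**The case against.** The best defence is that 7.6 does address bias. It delays the interview until follow-up is complete, six months after therapy ends, and it excludes the individual therapist. That stands: a reader might infer that the therapist exclusion is the only safeguard, and it is not. But the delay does not settle which interviewer rule applies, and it does not close the group gap.

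A reader might also infer that group therapists are meant to interview their own patients, or that three of the four clinicians will be free to do so. The documents do not support either. No section says who leads the groups, and the figure of three rests on the assumptions in the working.

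Nor do the documents show that the study's main conclusion would rest on these interviews. The overall aim has three parts: acceptability, feasibility and potential benefits. Feasibility is judged on recruitment, consent, attendance, loss to follow-up and drop-out, which do not depend on the interviewer. Section 11.1 calls change in personality functioning and social isolation the main objective. Part of the 7.6 interview concerns the questionnaires and the experience of research, where a treating clinician's influence matters less.

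Finally, the resource point is fair. The funding section lists only support in kind and no lived-experience interviewer time, section 7.1.3 treats the NIHR bid as undecided, and the two lived-experience contributors listed are not named as interviewers. This argues for a defined fallback; it does not justify leaving treating clinicians in the permitted set.

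**Conclusion.** The point holds. Sections 3.1 and 7.6 contradict each other on who conducts the acceptability interviews, and the exclusion in 7.6 omits clinicians who treated the participant in the group. As written, treating clinicians may collect data on an outcome that 3.1 and 3.7 call primary.

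The contradiction and the gap rest on the text alone. That answers would lean towards approval is a judgement about interviews by treating staff; the documents neither show it nor allow it to be sized. The effect is confined to the acceptability component and the adaptations drawn from it. This should be corrected before interviews begin, but it does not undermine the feasibility metrics or the weekly questionnaires.

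The status of acceptability is a separate inconsistency. A reader might think that deleting the entry in 3.6 would make acceptability primary throughout. It would not, because the trial summary and 3.4 would still name only personality functioning and social isolation.

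**What to change.** - In 7.6, state that the lived-experience researchers of 3.1 conduct the acceptability interviews.
- Extend the exclusion to any clinician who delivered individual or group MBT to that participant, and apply it to the exit interviews in 7.7 as well.
- If a fallback is needed, name it: a team member who did not treat the participant.
- Separately, give acceptability one status and use it in the trial summary and in 3.1, 3.4, 3.6 and 3.7.

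These are wording changes. The cost is less freedom in scheduling and reliance on the lived-experience interviewers being available, which the documents do not show to be secured. The fallback limits that risk.

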7.7 Withdrawal criteria

Participants can withdraw from the trial at any time, for any reason. They may choose to withdraw from different elements of the trial including:

- Withdrawal from MBT treatment only.
- Withdrawal from data collection.
- Withdrawal from the qualitative interviews.
- Withdrawal from any analysis of data from the participant's medical records.

If the participant wishes to withdraw, then they can do so at any time. If it is made clear, their rationale for withdrawing will be recorded and stored securely, and this will be made clear in the final report of the study. Participants may be replaced if the dropout rate is such that the statistical power of the study will be negatively impacted. This will increase the length of the trial, and as such an amendment from the REC will need to be sought, if the anticipated length of the trial will exceed 3 years.

Any participants that withdraw from the trial will be asked if they would like to continue to be involved in data collection, and follow up. They can withdraw from this aspect of the study.

If there are multiple severe adverse events, the trial may be stopped, if there is a direct link between the study and the adverse event.

In the event of a participant withdrawing from the study, they will be asked if the data collected to that point can be continued to be used in the data analysis. If they withdraw consent for their data to be used, it will be destroyed. All participants that withdraw will be offered an exit interview, using the theoretical framework of acceptability. Participants can refuse this interview with no impact to their clinical care. Participants can withdraw from the study but continue to access the treatment.

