7.1 Recruitment

Participants will come from a Later Life MBT service in Manchester, which exclusively serves older adults and offers a comprehensive MBT program. The study aims to collect data from 10 older adults for an 18-month treatment duration. As the population is likely to have multiple physical comorbidities, the study will aim to recruit 14 participants, with the expectation that there will be some attrition in the screening and introductory phases.

Single Case Experimental Design studies consider several factors for power, including participant count, observations, inter-participant correlation, and the likelihood of false positives (Shadish et al., 2014). To ensure adequate power, we'll collect weekly outcome data on personality functioning using the LPFS 2.0 and data on loneliness using the Social Isolation Short Form 4a before, during and after the 18 months treatment from the participants.

Participants will be sourced from an existing later life MBT service. All will have a confirmed personality disorder diagnosis based on the DSM-5 structured clinical interview (SCID-5-PD) or subthreshold. Those not meeting this criteria will not be excluded from the service if MBT is clinically indicated. When participants fulfil only one criterium under the cutoff point at the SCID5-PD interview, they will also be included in the study, but it will be clearly indicated that they are 'sub-threshold' to a full diagnosis of personality disorder.

Typically, referrals to the later life MBT service come from older adult community-based mental health teams in England, overseen by the NHS. All study participants will receive standard treatment, including regular meetings with a mental health professional and periodic reviews with a consultant psychiatrist. No restrictions will be placed on participants seeking other treatments, though concurrent psychological treatments might be contraindicated.

All participants will be aged 65 or older, with no upper age limit. The study won't control for other demographics, except that participants must reside in Manchester. Free transport can be arranged for participants, and in rare cases, treatment can be provided at home or in hospital wards due to frequent treatment disruptions from physical ailments or illnesses in older adults.

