10.7 Participant population

Data of patients who agree to participate in the study will be used for data-analysis. If the patient wants to stop participating in the study the patient will be asked if we can use the collected data up to and including that point in time.

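### Section 7.7 lets leavers be replaced with no trigger or counting rule and settles the fate of their scores at exit, so the drop-out rate is left open and the group result can tilt towards stayers

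*Protocol*

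**What the plan says.** Replacement: section 7.7 states that "Participants may be replaced if the dropout rate is such that the statistical power of the study will be negatively impacted". No number defines the trigger. The protocol does not say whether a replaced person stays in the drop-out denominator or how the replacement is counted. Section 7.1 sets the target: "The study aims to collect data from 10 older adults for an 18-month treatment duration". It plans to recruit 14 to reach it.

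Outcomes: section 3.1 lists among the primary feasibility measures the "proportion of participants lost to follow-up, number of sessions attended, and drop out rate".

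Scores already collected: under section 7.7, people who withdraw are handled at exit: "they will be asked if the data collected to that point can be continued to be used in the data analysis". The next rule is "If they withdraw consent for their data to be used, it will be destroyed". Section 10.7 repeats the request, for scores to the time of leaving: "If the patient wants to stop participating in the study the patient will be asked if we can use the collected data up to". Section 7.2 sets the general rule, "Data and samples collected up to the point of withdrawal can only be used after withdrawal if the participant has consented for this", and adds "Any intention to utilise such data should be outlined in the consent literature".

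Safeguards: section 7.7 treats leaving MBT and leaving data collection as separate choices. It invites anyone who withdraws to carry on with data collection and follow-up, offers an exit interview, and reports reasons for leaving where they are known.

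**The concern.** Two rules act together. The first allows new people to be brought in because drop-out is high, and drop-out is itself something the study sets out to measure. Without a counting rule, the reported rate depends on a choice made later. Section 2 says the study is to inform a future RCT, and drop-out is one of the main figures such a trial is planned on.

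The second makes a leaver's existing weekly scores depend on a decision at the point of leaving. If people who benefit less are more likely to leave, and some of them do not agree to their scores being used, the group result describes those who stayed and agreed. Section 3.4 reads significant falls on both scales as showing that MBT is effective, and there is no control group. Scores once destroyed cannot be recovered by any later analysis plan.

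**Working it through.** **1. The plan's own power figure.** Section 10.1 gives power close to 1 with 10 participants and d = 1. It was checked by simulation, 300 runs per setting. Each participant had 8 baseline and 72 treatment scores (Appendix 4) and a shift of d = 1. A one-sided permutation test was applied after thinning the series for autocorrelation, and the individual p-values were combined by their sum. Alpha 0.05 and lag-1 autocorrelations of 0, 0.3 and 0.5 are assumptions. With 10 participants, power is 1.00 at all three, so the figure reproduces.

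**2. What replacement would protect.** The same simulation with fewer people, at autocorrelation 0 / 0.3 / 0.5:
- 6 participants: 1.00 / 1.00 / 0.99
- 5 participants: 1.00 / 0.99 / 0.92
- 4 participants: 1.00 / 0.98 / 0.88

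On the protocol's inputs, power barely moves until fewer than six remain, so the trigger has no clear meaning. This assumes the same d = 1 in everyone, and a smaller true effect would cost more. A paired t-test on person-level differences, which is not the planned test and uses a different d, gives 0.80 two-sided at 10 and 0.51 at 6.

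**3. Drop-out denominator.** Suppose four of 14 leave and four replacements all stay.
- Original cohort: 4/14 = 28.6%
- All entrants: 4/18 = 22.2%

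If replacements left at the same rate, the expected count would be 4 + 4 × 4/14 = 5.14, and 5.14/18 = 28.6%. The gap therefore arises when replacements happen to stay, or differ from the first entrants. The protocol does not say which figure is reported.

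**4. Possible drift in the effect.** The documents give neither a drop-out rate after baseline nor an effect in leavers, so this is an illustration. Let 10 stayers gain d = 1 and four leavers gain g. The mean over all entrants is (10 × 1 + 4g)/14.
- g = 0: 10/14 = 0.71, overstatement 1.00 − 0.71 = 0.29
- g = 0.25: 11/14 = 0.79, overstatement 0.21
- g = 0.5: 12/14 = 0.86, overstatement 0.14

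These overstatements apply if no leaver's scores are kept. With g = 0 and k of the four leavers kept, the estimate is 10/(10 + k): 1.00, 0.91, 0.83, 0.77 and 0.71 for k = 0 to 4. Keeping all four removes the bias. If leaving is unrelated to response, there is none at any k.

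**5. Effect on the group p-value.** Adding four leavers with no effect to 10 stayers left simulated power at 1.00 (autocorrelation 0 and 0.3). At d = 1 the drift concerns the size and reading of the effect, not whether the group test is significant.

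**6. Calendar.** One month to the introductory-group notice, 12 weeks of group, 8 weeks of baseline, 18 months of treatment and 6 months of follow-up give 1 + 20/4.345 + 24 = 29.6 months. A replacement finishes within 3 years only by entering in about the first 36 − 29.6 = 6.4 months.

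**The case against.** The strongest reply is that leaving MBT need not end a person's scores. Section 7.7 separates the two and invites leavers to continue, and section 10.7 keeps the data of those who agree. This stands and lowers the risk. It does not remove it, because each safeguard depends on the leaver's willingness at that moment.

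Several stronger readings are tempting and are not supported:
- A reader might infer that scores are destroyed unless the leaver agrees. The text makes them unusable without consent (section 7.2) and orders destruction only when consent for use is withdrawn (section 7.7). Honouring a refusal is right and is not a statistical error.
- A reader might infer that replaced people are excluded from the group p-value. Section 10.3.2 contains no such rule, and section 10.7 points the other way for those who agree.
- A reader might apply the whole fall from 14 to 10 to the weekly scores. Section 7.1 expects that attrition during screening and the introductory group, before weekly scoring starts. Section 10.1 is looser, but four losses after baseline is an assumption.
- A reader might foresee drop-out reported as 0/14. That needs leavers removed from the denominator, which no section says. Drop-out is a primary outcome, and section 10.8 intends to describe the reasons.

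It can also be said that the analysis is mainly within-person, so one departure does not change another person's result. That is true of the individual tests, but the group p-value still depends on who contributes.

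Finally, the consent form and the feasibility table mentioned in section 3.1 were not available to this review. The form may already take retention consent at enrolment, and the table may define denominators. If so, sections 7.7 and 10.7 need only be brought into line.

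**Conclusion.** The point holds as a weakness in two stated conduct rules. Replacement is permitted on a primary outcome with no trigger or counting rule, and the fate of collected scores is put to the participant at exit. The firm consequence is a drop-out rate that depends on an unstated denominator, for example 29% against 22%.

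The tilt in efficacy is a conditional risk: 0.14 to 0.29 d if stayers gain d = 1, four of 14 leave after baseline gaining 0 to 0.5, and none of their scores are kept. It is zero if leaving is unrelated to response or leavers' data are kept. Replacement is hardly needed for power at the planned effect, since simulated power is at least 0.99 with six participants under the assumed alpha and autocorrelations. Because most replacements would need an extension beyond 3 years, the rule may seldom be used, but as written its use is discretionary.

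**What to change.** (a) In section 7.7, state that later entrants are additional participants and not replacements. Everyone who consented stays in the recruitment and loss-to-follow-up denominators, and everyone who started treatment stays in the treatment drop-out denominator. Report original and additional participants separately as well as together.

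(b) In sections 7.2, 7.7 and 10.7 and in the consent form, take consent at enrolment to keep and analyse scores collected up to withdrawal, as section 7.2 already foresees. Destroy them only on explicit request, and always keep the anonymous count of withdrawals.

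(c) In section 10.3.2, confirm that the group p-value uses every participant with analysable baseline and treatment-phase scores, whether or not they completed, with a completers-only result as secondary.

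The cost is one amendment to the protocol and consent form and one secondary analysis, with no added visits and no added participants. The drawback is that the effect and drop-out figures may look less favourable, and completers may number fewer than 10.
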